#### 5.1.1 Part A (COMPLETED)

Nivolumab of 3 mg/kg IV infused over 60 minutes every 14 days. A cycle will be considered 28 days. If Dose Level 1 is not tolerable, then the 3 mg/kg dose will be deescalated to 1 mg/kg and a similar cohort of patients will be evaluated for tolerability at this dose. Note: In the event that dose-limiting immune-related toxicities are observed in two patients enrolled on Part A that would potentially define the MTD as less than the adult RP2D, a review by COG, CTEP, and BMS

will be scheduled before proceeding with dosing changes.

Dose Level	Nivolumab (mg/kg) IV over 60 min.	Day(s) of Administration
-1	1	1, 15
1*	3	1, 15

\*Starting dose

Update: The single-agent recommended Phase 2 dose of Part A was determined to be 3 mg/kg nivolumab.

### 5.1.2 Part B (COMPLETED)

Part B will evaluate the activity of nivolumab at its RP2D in expanded cohorts for patients with neuroblastoma, osteosarcoma, rhabdomyosarcoma, Ewing sarcoma, Hodgkin lymphoma, non-Hodgkin lymphoma. In the melanoma cohort (Part B7), toxicities and disease response will be reported descriptively within the confines of a Phase 1/2 study.

Dose Level	Nivolumab (mg/kg) IV over 60 min.	Day(s) of Administration
1	3	1, 15

### 5.1.3 Part C (COMPLETED)

Part C will enroll all histologies with the goal of identifying the MTD or RP2D of the combination of nivolumab and ipilimumab. The combination of nivolumab and ipilimumab will be administered every 3 weeks X 4 followed by nivolumab given every 2 weeks until off protocol criteria in [Section 10.1](#) are met. **Note that cycle length is 21 days for the first 4 cycles of Part C, whereas reverts to 28 days for subsequent cycles which comprises two doses of nivolumab, and is the same regimen used in Part A and B.**

Dose Level	Cycles 1-4	Cycles 5+
1	Nivolumab (IV over 60 min) 1 mg/kg on Day 1  Ipilimumab (IV over 90 min) 1 mg/kg on Day 1	Nivolumab (IV over 60 min) 3 mg/kg on Days 1 and 15
2	Nivolumab (IV over 60 min) 3 mg/kg on Day 1  Ipilimumab (IV over 90 min) 1 mg/kg on Day 1	Nivolumab (IV over 60 min) 3 mg/kg on Days 1 and 15

Infusion of ipilimumab (over 90 minutes) should be initiated no sooner than 30 minutes after completion of the nivolumab infusion.

Vital signs (temperature, pulse, blood pressure and respirations) will be monitored closely baseline then every 15 minutes x 2, then every 30 minutes x 3 beginning at the initiation of administration of ipilimumab infusion. Patients who develop symptoms or signs of hypotension ( $\geq 25\%$  decrease in systolic or diastolic blood pressures from baseline) that are temporally related to ipilimumab infusion will receive additional IV fluids as appropriate until the signs and symptoms resolve. During cycle 1, patients must remain for observation for a total of 6 hours following completion of ipilimumab. The post administration observation period may be extended to 24 hours and the patient admitted if clinically indicated. If the patient

tolerates the first infusion of ipilimumab without incident, the observation period may be reduced to 90 minutes following completion of the drug infusion with subsequent cycles. Any patient who develops Grade 3 or 4 anaphylaxis felt to be primarily related to administration of ipilimumab will be removed from protocol therapy.

Protocol therapy will continue to be administered until patient meets one of the off protocol criteria in [Section 10.1](#).

Update: The recommended Phase 2 dose of nivolumab in combination with ipilimumab from Part C was determined to be 3 mg/kg nivolumab and 1 mg/kg ipilimumab.

#### 5.1.4 Part D (COMPLETED)

If criteria for accrual to Part D are met, the combination of nivolumab and ipilimumab will be administered every 3 weeks X 4 followed by nivolumab given every 2 weeks until off protocol criteria in [Section 10.1](#) are met. **Note that cycle length is 21 days for the first 4 cycles of Part D, whereas reverts to 28 days for subsequent cycles which comprises two doses of nivolumab, and is the same regimen used in Part A and B.**

Dose Level	Cycles 1-4	Cycles 5+
1	Nivolumab (IV over 60 min) 3 mg/kg on Day 1  Ipilimumab (IV over 90 min) 1 mg/kg on Day 1	Nivolumab (IV over 60 min) 3 mg/kg on Days 1 and 15

Infusion of ipilimumab (over 90 minutes) should be initiated no sooner than 30 minutes after completion of the nivolumab infusion.

Vital signs (temperature, pulse, blood pressure and respirations) will be monitored closely baseline then every 15 minutes x 2, then every 30 minutes x 3 beginning at the initiation of administration of ipilimumab infusion. Patients who develop symptoms or signs of hypotension ( $\geq 25\%$  decrease in systolic or diastolic blood pressures from baseline) that are temporally related to ipilimumab infusion will receive additional IV fluids as appropriate until the signs and symptoms resolve. During cycle 1, patients must remain for observation for a total of 6 hours following completion of ipilimumab. The post administration observation period may be extended to 24 hours and the patient admitted if clinically indicated. If the patient tolerates the first infusion of ipilimumab without incident, the observation period may be reduced to 90 minutes following completion of the drug infusion with subsequent cycles. Any patient who develops Grade 3 or 4 anaphylaxis felt to be primarily related to administration of ipilimumab will be removed from protocol therapy.

#### 5.1.5 Part E

The combination of nivolumab 1 mg/kg and ipilimumab 3 mg/kg will be administered every 3 weeks X 4 followed by nivolumab 3 mg/kg administered every 2 weeks until off protocol criteria in Section 10.1 are met. Note that cycle length is 21 days for the first 4 cycles of Part E; in cycle 5 and for subsequent cycles, cycle length will be 28 days and nivolumab 3 mg/kg will be administered

on days 1 and 15 of each cycle.

Dose Level	Cycles 1-4 (21-day Cycles)	Cycles 5+ (28-day Cycles)
1	Nivolumab (IV over 30 min) 1 mg/kg on Day 1  Ipilimumab (IV over 90 min) 3 mg/kg on Day 1	Nivolumab (IV over 30 min) 3 mg/kg on Days 1 and 15

Infusion of ipilimumab (over 90 minutes) should be initiated no sooner than 30 minutes after completion of the nivolumab infusion. If nivolumab therapy is withheld, ipilimumab should also be withheld.

Vital signs (temperature, pulse, blood pressure and respirations) will be monitored closely baseline then every 15 minutes x 2, then every 30 minutes x 3 beginning at the initiation of administration of ipilimumab infusion. Patients who develop symptoms or signs of hypotension ( $\geq 25\%$  decrease in systolic or diastolic blood pressures from baseline) that are temporally related to ipilimumab infusion will receive additional IV fluids as appropriate until the signs and symptoms resolve. During cycle 1, patients must remain for observation for a total of 6 hours following completion of ipilimumab. The post administration observation period may be extended to 24 hours and the patient admitted if clinically indicated. If the patient tolerates the first infusion of ipilimumab without incident, the observation period may be reduced to 90 minutes following completion of the drug infusion with subsequent cycles. Any patient who develops Grade 3 or 4 anaphylaxis felt to be primarily related to administration of ipilimumab will be removed from protocol therapy.

5.2 **Protocol therapy will continue to be administered until patient meets one of the off protocol criteria in [Section 10.1](#). Criteria for Starting Subsequent Cycles**

A cycle may be repeated every 28 days for Parts A and B (and either every 21 days or 28 days for Parts C, D, and E) if the patient has again met the parameters as defined in the eligibility section, [Section 4.0](#), has not met any of the criteria for removal from therapy per [Section 10.1](#), and has not experienced a dose-limiting toxicity. A delay of up to 7 days from the date of the next scheduled treatment dose may be allowed. Please note the following exceptions:

- Patients may continue on to the next cycle if Pancreatic Function is  $\leq$  Grade 1 (See [Section 6.5](#))
- Patients who experience pleural effusion may continue onto the next cycle upon resolution as per [Section 6.8](#).

5.3 **Grading of Adverse Events**

Adverse events (toxicities) will be graded according to the NCI Common Terminology Criteria for Adverse Events (CTCAE) version 5.0. All appropriate treatment areas should have access to a copy of the CTCAE version 5.0. A copy of the CTCAE version 5.0 can be downloaded from the CTEP web site [http://ctep.cancer.gov/protocolDevelopment/electronic\\_applications/ctc.htm](http://ctep.cancer.gov/protocolDevelopment/electronic_applications/ctc.htm). Any suspected or confirmed dose-limiting toxicity should be reported immediately (within 24 hours) to the Study Chair.

5.4 **Definition of Dose-Limiting Toxicity (DLT)**

DLT will be defined as any of the following events that are possibly, probably, or definitely attributable to protocol therapy. DLT definitions will be the same for all parts. The DLT

observation period for the purposes of dose-escalation in Part C or dose de-escalation in Part A will be the first cycle of therapy. Toxicities with subsequent cycles will be monitored carefully and if significant numbers of delayed toxicities are observed, consideration will be given to a protocol amendment to focus on delayed toxicities in assessing the MTD.

#### 5.4.1 Non-Hematological DLT:

- Any Grade 3 or Grade 4 non-hematological toxicity attributable to protocol therapy with the specific exclusion of:
  - a. Grade 3 ALT that returns to levels that meet initial eligibility criteria or baseline within 7 days and does not require systemic immunosuppression. **Note:** For the purposes of this study the ULN for ALT is defined as 45 U/L. Adverse event grades will be based on increases above the upper limit of normal, regardless of the subject's baseline. See [Appendix IX](#) for toxicity grading table.
  - b. Grade 3 liver enzyme elevation, including AST/SGT that returns to baseline within 7 days and does not require systemic immunosuppression.
  - c. Grade 3 or 4 serum electrolyte or mineral abnormalities responsive to supplementation.
  - d. Grade 3 or 4 amylase or lipase abnormalities that are not associated with diabetes mellitus (DM), associated liver or gall bladder inflammation clinical manifestations of pancreatitis and which decrease to  $\leq$  Grade 2 within 7 days.
  - e. Grade 3 rash/oral lesions that resolves to Grade  $\leq$  1 within 7 days
  - f. Fever greater than 40°C of  $\leq$  24 hr duration
  - g. Grade 3 fatigue that resolves to Grade  $\leq$  2 within 7 days
  - h. Grade 3 creatinine increased that resolves to Grade  $\leq$  1 or baseline within 7 days
  - i. Grade 3 pleural effusion that resolves per [Section 6.8](#)
- Grade 2 fever that does not resolve to Grade  $\leq$  1 within 7 days
- Grade 2 uveitis, eye pain, or blurred vision that does not respond to topical therapy and does not improve to Grade 1 prior to next scheduled dose
- Grade 2 non-hematological toxicity requiring systemic immunosuppressive therapy, including but not limited to, autoimmunity of the lung, heart, kidney, bowel, CNS, pituitary or eye, with the specific exclusion of:
  - a. Grade 2 pleural effusion that resolves per [Section 6.8](#)
  - b. Drugs will be held for grade 2 cardiac dysfunction pending evaluation.
- Grade 2 endocrine toxicity requiring hormone replacement, with the exception of Grade 2 hypothyroidism, thyroiditis and thyroid dysfunction adequately managed with thyroid hormone replacement (see [Section 6.11](#))
- Grade 2 adrenal insufficiency
- Parts A and B: Grade 2 colitis or Grade 2 diarrhea attributable to protocol therapy that persists for  $>$  7 days will be considered a DLT.
- Parts C, D, and E: Grade 2 colitis or Grade 2 diarrhea attributable to protocol therapy of any duration will be considered a DLT.
- Any non-hematological toxicity requiring  $>$  7 days delay in therapy will be considered a DLT

- Note: Allergic reactions that necessitate discontinuation of study drug will not be considered a dose-limiting toxicity.

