### 6.2 Dose Modifications for Non-Hematological Toxicity

Patients who have any dose-limiting non-hematological toxicity as defined in [Section 5.4.1](#) will be removed from protocol therapy, except as outlined in Sections 6.3-6.12 below.

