**6.14 Dose Modifications for Nivolumab + Ipilimumab Cardiac Toxicities**

Cardiac Toxicities *	Nivolumab + Ipilimumab Cardiac Toxicities
≤ Grade 1	Hold dose pending evaluation and observation.** Evaluate for signs and symptoms of CHF, ischemia, arrhythmia or myositis. Obtain history EKG, CK (for concomitant myositis), CK-MB. Repeat troponin, CK and EKG 2-3 days. If troponin and labs normalize may resume therapy. If labs worsen or symptoms develop then treat as below. Hold pending evaluation.
Grade ≥ 2 with suspected myocarditis	Hold dose.** Admit to hospital. Cardiology consult. Rule out MI and other causes of cardiac disease. Cardiac Monitoring. Cardiac Echo. Consider cardiac MRI and cardiac biopsy. Initiate high dose methylprednisolone. If no improvement within 24 hours, add either infliximab, ATG or tacrolimus. Resume therapy if there is a return to baseline and myocarditis is excluded or considered unlikely.
Grade ≥ 2 with confirmed myocarditis	Off protocol therapy. Admit to CCU (consider transfer to nearest Cardiac Transplant Unit). Treat as above. Consider high dose methylprednisolone Add antithymocyte globulin (ATG) or tacrolimus if no improvement. Off treatment.

*Including CHF, LV systolic dysfunction, Myocarditis, CPK, and troponin  **Patients with evidence of myositis without myocarditis may be treated according as "other event"
 
Note: The optimal treatment regimen for immune mediated myocarditis has not been established. Since this toxicity has caused patient deaths, an aggressive approach is recommended.
	

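### Section 6.14 lets therapy restart after suspected myocarditis of Grade 2 or higher without asking whether the event was a DLT, although Sections 6.2 and 5.2 end therapy after a DLT

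*Combined protocol and SAP*

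**What the plan says.** All references are to the combined protocol and SAP.

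- **Section 5.4.1, Grade 3 and 4.** The DLT definition covers "Any Grade 3 or Grade 4 non-hematological toxicity attributable to protocol therapy with the specific exclusion of" nine items, a to i. None is cardiac. Section 5.4 requires only possible attribution.
- **Section 5.4.1, Grade 2.** A further bullet makes a DLT of "Grade 2 non-hematological toxicity requiring systemic immunosuppressive therapy, including but not limited to, autoimmunity of the lung, heart, kidney, bowel" and other sites, again with listed exclusions. Item a excludes a resolving pleural effusion. Item b reads "Drugs will be held for grade 2 cardiac dysfunction pending evaluation".
- **Section 6.2.** Patients with a non-hematological DLT "will be removed from protocol therapy, except as outlined in Sections 6.3-6.12 below".
- **Section 5.2.** A new cycle requires that no DLT has occurred. The listed exceptions concern pancreatic function and pleural effusion only.
- **Section 6.14.** The row "Grade ≥ 2 with suspected myocarditis" holds the dose, then instructs "Initiate high dose methylprednisolone. If no improvement within 24 hours", add a second immunosuppressant. It closes with "Resume therapy if there is a return to baseline and myocarditis is excluded or considered unlikely". A separate row takes confirmed myocarditis off therapy. The table's footnote gives its scope as "Including CHF, LV systolic dysfunction, Myocarditis, CPK, and troponin".

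**The concern.** A site managing a Grade 3 or 4 cardiac event will look up the cardiac table. That table permits restart on two conditions, and neither concerns DLT status. If the event is still at least possibly due to the study drugs, Sections 6.2 and 5.2 require the opposite. The stake is patient safety: a patient could be re-treated after a cardiac DLT, and Section 6.14 itself notes that immune-mediated myocarditis has been fatal.

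Item b in Section 5.4.1 is a smaller drafting fault in the same area. It sits in a list of DLT exclusions but tells the site to hold drug. Unlike item a, it names no excluded event and no resolution condition.

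**Working it through.** The plan attaches no figure to this point, so the check is a comparison of the texts.

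**Step 1: is a Grade 3 or 4 cardiac event a DLT?** Yes, if at least possibly attributable. Exclusions a to i cover ALT, other liver enzymes, electrolytes, amylase or lipase, rash or oral lesions, fever, fatigue, creatinine and pleural effusion.

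**Step 2: what follows from a DLT?** Removal under 6.2. Its exceptions run from 6.3 to 6.12, which leaves out 6.13 and 6.14. Section 6.13 (renal) closes the gap by referring back to 6.2 whenever the DLT definition is met. Section 6.14 has no such reference. Section 5.2 independently bars the next cycle.

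**Step 3: does the 6.14 row reach Grade 3 and 4?** Yes, because it has no upper limit. Eleven of the sections from 6.3 to 6.14 carry a Grade 4 rule (6.9 does not). Ten end therapy at Grade 4: 6.5 because its liver exceptions in 5.4.1 stop at Grade 3, and 6.10 apart from decreased tendon reflex. Only 6.14 allows restart. This suggests an oversight; it measures no consequence.

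**Step 4: does setting myocarditis aside settle attribution?** No. If the work-up finds another cause, the event is not a DLT and there is no conflict. But the row tests only whether myocarditis is excluded or unlikely, and the table also covers heart failure, ventricular dysfunction and raised enzymes. Section 9.1.9 lists cardiomyopathy and pericarditis, apart from myocarditis, as possibly related to nivolumab. An event can therefore pass the 6.14 test and remain possibly attributable.

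**Step 5: is any window left after the other limits?** Section 5.2 requires Section 4.0 to be met again and allows a delay of at most 7 days. Section 4.2.2.1 bars systemic corticosteroids in the preceding 7 days. In a 21-day Part E cycle the next dose falls on day 22, or day 29 with the full delay. Counting days as Section 4.0 does, the last steroid dose must then fall by:

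- day 22 − 7 = day 15 without delay;
- day 29 − 7 = day 22 with the full delay.

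If the 14-day interval that 4.2.2.1 sets for steroids given for earlier immune events is applied instead, these become day 8 and day 15. A delay beyond 7 days is itself a DLT under 5.4.1. The window is narrow but not empty.

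**Step 6: Grade 2.** On the plain text of 5.4.1, an attributable Grade 2 cardiac event that requires systemic immunosuppression is already a DLT, because the bullet names the heart. Item b states nothing that would remove it.

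**The case against.** The strongest reply is that the text already supplies an order of precedence. Section 6.2 names its exceptions and 6.14 is not among them; 5.2 makes freedom from DLT a condition of every new cycle; 10.1 repeats removal for adverse events under 5.4 and 6.0. Read together, the 6.14 restart applies only to patients whom those sections have not removed. That is the better reading, and it stands. What remains is that the cardiac table does not say so, while the renal section beside it does.

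Oversight also counts. Suspected DLTs go to the Study Chair within 24 hours (5.3), dosage modifications must be notified (6.0), and in Part E the study committee reviews attributed Grade 3 to 5 toxicity weekly (11.7.1). For patients with a cardiac history or risk, 4.2.7 adds function thresholds at re-eligibility. These lower the chance of re-treatment without correcting the instruction.

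The attribution case is narrower than 6.14's footnote suggests. Section 9.1.9 also places heart failure among events with insufficient evidence of causation by nivolumab, and 9.2.8 does the same for restrictive cardiomyopathy with ipilimumab. The row applies only where myocarditis was suspected and other cardiac causes are being ruled out. Individual attribution can still be possible, which is all that 5.4 asks.

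**Conclusion.** The point holds as a minor inconsistency in the dose-modification rules. It applies where a Grade 3 or 4 cardiac event in the suspected-myocarditis row returns to baseline, myocarditis is excluded or thought unlikely, the event remains at least possibly attributable, and the limits in Step 5 are met. The documents give no frequency for this, so no size is put on it.

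Three stronger readings are tempting and are not supported:

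- **That the rules cannot be reconciled, or that 6.14 overrides.** Sections 6.2 and 5.2 state their own exceptions and are best read as controlling.
- **That item b exempts Grade 2 cardiac toxicity from the DLT count.** Only its position suggests this. Its words exclude nothing, and the parent bullet names the heart.
- **That the restart conflict changes the chance of closing Part E.** One Cycle 1 DLT among the first 10 patients does close Part E under 11.7.1. But an attributable Grade 3 or 4 cardiac event is a DLT whether or not the patient restarts, so the count is the same either way. The closing probabilities stated there do not bear on this point.

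**What to change.** In the Section 6.14 row for suspected myocarditis, change the last sentence so that therapy may resume *only if the event does not meet the DLT definition in Section 5.4.1*, and keep the two existing conditions after it. This brings the row into line with 6.2 and 5.2, and it covers Grade 2 events that are DLTs as well as Grade 3 and 4.

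As an accompanying editorial correction, delete item b from the Grade 2 exclusion list in Section 5.4.1. The hold instruction already stands in 6.14.

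Do not add 6.14 to the exceptions in 6.2. The row has no upper grade, so that would exempt Grade 3 and 4 cardiac DLTs from removal.

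The cost is one reworded sentence and one deleted line in an amendment. No visits, data or patients are added, and no estimate, test or stopping boundary changes. Where the plain text is already followed, DLT classification stays the same. Where a site had taken item b as an exclusion, the Grade 2 event would now count as a DLT.

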#### 5.4.2 Hematological DLT:

In patients evaluable for hematological toxicity (see [Section 4.1.7.1](#)) DLT is defined as:

- Grade 4 thrombocytopenia (platelet count < 25,000/mm^3) or Grade 4 neutropenia lasting at least five days.
  - **Note:** Grade 3 or 4 febrile neutropenia will not be considered a dose-limiting toxicity. Any grade lymphopenia will not be considered DLT.

## 6.0 DOSE MODIFICATIONS FOR ADVERSE EVENTS

**The Study Chair must be notified of any dosage modification or use of myeloid growth factor.**

### 6.1 Dose Modifications for Hematological Toxicity

Patients who experience dose-limiting hematological toxicity as defined in [Section 5.4.2](#) will be removed from protocol therapy.

### 6.2 Dose Modifications for Non-Hematological Toxicity

Patients who have any dose-limiting non-hematological toxicity as defined in [Section 5.4.1](#) will be removed from protocol therapy, except as outlined in Sections 6.3-6.12 below.

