Grade 3	Off protocol therapy unless DLT exception in Section 5.4.1 is met.
Grade 4	Off protocol therapy unless DLT exception in Section 5.4.1 is met.
See Appendix IX for values that represent thresholds between CTCAE grades. Continued treatment of active immune mediated hepatitis may exacerbate ongoing inflammation. Holding drug to evaluate LFT changes and early treatment are recommended.	
LFT changes may occur during steroid tapers from other events and may occur together with other GI events including cholecystitis/pancreatitis.	
Recommended management: see for Hepatic AE management algorithm	

Pancreatitis; Amylase/Lipase	Management/Next Dose of Nivolumab ± Ipilimumab
≤ Grade 1	Continue protocol therapy
Grade 2 Amylase	Continue protocol therapy
Grade 2 Pancreatitis/Lipase	Hold until resolution to ≤ Grade 1; Resume at same dose level if asymptomatic
Grade 3	Off protocol therapy unless DLT exception in Section 5.4.1 is met.
Grade 4	Off protocol therapy
Patients may develop symptomatic and radiologic evidence of pancreatitis as well as DM and DKA. Lipase elevation may occur during the period of steroid withdrawal and with other immune mediated events or associated with colitis, hepatitis, and patients who have asymptomatic lipase elevation typically have self-limited course and may be retreated. For treatment management of symptomatic pancreatitis please follow the Hepatic Adverse Event Management Algorithm below	

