#### 6.11 Dose Modifications for Endocrine Adverse Events

Endocrine Hypophysitis; Adrenal Insufficiency	Management/Next Dose of Nivolumab ± Ipilimumab
≤ Grade 1	Continue protocol therapy; See Endocrine Management Algorithm
Grade 2	Off protocol therapy if DLT criteria in Section 5.4.1 is met.
Grade 3	Off protocol therapy
Grade 4	Off protocol therapy

Note all patients with symptomatic pituitary enlargement, exclusive of hormone deficiency, but including severe headache or enlarged pituitary on MRI should be considered grade 3 events. Isolated thyroid or testosterone deficiency may be treated as grade 2 if there are no other associated deficiencies and adrenal function is monitored. Please evaluate pituitary function before beginning steroid therapy or replacement therapy of any kind.
	
Recommended management: See Endocrine Management Algorithm	

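### Section 6.14 tells sites to resume therapy after a resolved Grade 2 or higher suspected-myocarditis event with no DLT check, although Sections 5.2 and 6.2 require removal when that event was a DLT

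*Combined protocol and SAP*

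**What the plan says.** **Removal rule.** Under Section 6.2, patients with a non-hematological DLT "will be removed from protocol therapy, except as outlined in Sections 6.3-6.12 below". Sections 6.13 (renal) and 6.14 (cardiac) fall outside that range.

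**Next-cycle rule.** Section 5.2 allows a further cycle only if the patient again meets the eligibility parameters, has met no removal criterion, "and has not experienced a dose-limiting toxicity". It lists two exceptions, for pancreatic function and pleural effusion.

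**DLT definition.** Section 5.4 requires at least possible attribution to protocol therapy. Section 5.4.1 counts "Any Grade 3 or Grade 4 non-hematological toxicity attributable to protocol therapy", subject to nine exclusions (a to i), none of them cardiac. It also counts any non-hematological toxicity requiring more than "7 days delay in therapy will be considered a DLT". Its only cardiac text, placed under the Grade 2 immunosuppression criterion, says that drugs are held for Grade 2 cardiac dysfunction while it is evaluated.

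**Cardiac table.** Section 6.14 covers heart failure, left ventricular dysfunction, myocarditis, CPK and troponin. It has three rows:
- Grade 1 or lower: hold and evaluate; "If troponin and labs normalize may resume therapy".
- Grade 2 or higher, myocarditis suspected: hold, admit, work up, give high-dose methylprednisolone; "Resume therapy if there is a return to baseline and myocarditis is excluded or considered unlikely".
- Grade 2 or higher, myocarditis confirmed: off protocol therapy.

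**Other organ sections.** Section 6.5 has Grade 3 and 4 liver events "Off protocol therapy unless DLT exception in" Section 5.4.1 is met. Section 6.11 has Grade 2 endocrine events "Off protocol therapy if DLT criteria in" that section are met. Section 6.13 refers renal events to 6.2 when the DLT definition is met. Section 6.14 has no such link.

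**The concern.** A site managing a cardiac event will turn to the cardiac table. Its suspected-myocarditis row reads as a complete instruction: two conditions, then resume. Nothing in it sends the reader back to the DLT definition, and nothing limits it to Grade 2. A site that follows it could re-treat a child after an attributable Grade 3-4 cardiac event when the general rules allow no further treatment.

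This is a live issue. Part E is the only part not marked completed in Section 5.1, it gives the nivolumab-ipilimumab combination for which 6.14 is titled, and it uses the higher ipilimumab dose. Section 6.14 itself notes that immune-mediated myocarditis has caused deaths.

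**Working it through.** There is no figure to reproduce, so the check applies both sets of rules to the same patient. Unless stated, the event is at least possibly attributable and has returned to baseline.

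| Case | Section 6.14 | 5.4.1 with 6.2 and 5.2 | Conflict |
|---|---|---|---|
| 1. Grade 3-4, myocarditis suspected, then excluded or unlikely | Resume | DLT; remove | Yes |
| 2. Grade 2, same course, more than 7 days' delay required | Resume | DLT; remove | Yes |
| 3. Grade 2, same course, resolved within 7 days | Resume | Not a DLT on these two criteria | No |
| 4. Event judged unrelated or unlikely related | Resume | Not a DLT | No |
| 5. Grade 2 or higher, myocarditis confirmed | Remove | Not in tension with removal | No |
| 6. Grade 1 or lower, labs normalize | May resume | DLT only if more than 7 days' delay was required | Unlikely |

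**Case 1.** The Grade 3-4 criterion applies because no item in exclusions a to i is cardiac. Excluding myocarditis does not by itself make the event unattributable. Section 6.14 also covers heart failure, ventricular dysfunction, CPK and troponin, and the nivolumab risk list in Section 9.1.9 names cardiomyopathy and pericarditis separately from myocarditis. A judgment that myocarditis is unlikely can leave the event possibly attributable, which is enough under 5.4.

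**Cases 2 and 3.** For Grade 2 the point rests on the delay criterion alone. Section 5.4.1 also makes Grade 2 toxicity requiring systemic immunosuppression a DLT, but the Grade 2 cardiac line sits among the exclusions to that criterion and its wording leaves its effect unclear. The point does not rely on it.

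**Case 6.** Section 6.14 repeats the labs at 2-3 days and Cycles 1-4 last 21 days, so a delay of more than 7 days is improbable.

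**When 5.2 applies.** In Cycles 1-4 of Part E both drugs are given on Day 1 only, so resuming the combination always means starting a new cycle, and 5.2 bars it after a DLT. From Cycle 5 a Day 15 dose of nivolumab alone could be resumed within a cycle; there 6.2 is the operative bar.

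**Do other sections settle it?** Section 10.1(c) cites 5.4 and 6.0 together. Footnote 13 to the Section 8.1 table cites 5.4.1 beside a section printed as 6.1.4, apparently 6.14. Neither ranks them. The closed list in 6.2 and the DLT condition in 5.2 do: 6.14 is not among their exceptions.

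**The case against.** The strongest reply is that the documents already give the answer. Section 6.2 limits its exceptions to a list that omits 6.14, and 5.2 independently bars a further cycle after a DLT. A site reading 5.2, 6.2 and 6.14 together has one compliant course, which is removal. This stands. A reader might infer that the protocol leaves open which rule governs; the text does not support that.

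Other limits on resumption also count. Section 5.2 requires the eligibility parameters to be met again. Read literally, these include no systemic corticosteroids in the preceding 7 days (Section 4.2.2.1, worded for enrollment). Section 5.2 allows a delay of up to 7 days only. The Grade 2 cardiac line in 5.4.1 supports a harmonized reading in which Grade 2 is held, evaluated and possibly resumed, while attributable Grade 3-4 is a DLT.

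Oversight is substantial: DLT reports to the Study Chair within 24 hours (5.3), notification of dosage modifications (6.0), and weekly review of attributable Grade 3-5 toxicity (11.7.1) and of the Study Chair's DLT evaluations (14.5). One Cycle 1 DLT among the first 10 Part E patients closes the study (11.7.1), so a Cycle 1 cardiac event would have to be adjudicated.

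Finally, the range in 6.2 may simply not have been updated, in which case 6.14 was meant as an exception. The documents do not show the intent, so the fix must allow for either.

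These arguments narrow the point but do not remove it. They show that 6.14 should not be followed as written for DLT patients, yet the row still tells sites to do so. The Part E stopping rule counts Cycle 1 only and does not help with later events.

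**Conclusion.** The resume instruction in the suspected-myocarditis row of 6.14 is wrong as written for attributable cardiac events that are Grade 3-4 or require more than 7 days' delay. On a literal reading 6.2 and 5.2 prevail and the patient comes off therapy. It should be corrected because the section a site is most likely to consult says the opposite for a serious toxicity.

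The size is small. One of three rows is affected, and within it only events that are attributable, recover to baseline, have myocarditis excluded or considered unlikely, and meet one of the two DLT criteria. Part E enrolls at most 23 patients. The documents give no rate for this subset, so no frequency is claimed.

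Two stronger readings do not hold. A reader might infer that children with confirmed myocarditis could be re-treated; 6.14 removes them at Grade 2 or higher. A reader might also infer that Part E's DLT count or stopping rule is compromised; the DLT definition in 5.4.1 is the same whatever 6.14 says about resuming, so no error rate or sample size changes.

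The conclusion assumes that some events in this row remain at least possibly attributable after work-up.

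**What to change.** Add one sentence to the Grade 2 or higher suspected-myocarditis row of Section 6.14: *Therapy may resume only if the event does not meet the DLT definition in Section 5.4.1; otherwise Section 6.2 applies.* This follows the approach of Section 6.13. The Grade 1 or lower row needs no edit.

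If the sponsor does intend re-treatment after a resolved cardiac DLT, add 6.14 to the exceptions in both 6.2 and 5.2. Changing 6.2 alone would leave the bar in 5.2 in place.

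Leave 5.4.1 unchanged. As a clerical matter, the section printed as 6.1.4 in footnote 13 to the Section 8.1 table can be corrected to 6.14 in the same amendment.

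The cost is one sentence. The downside is that a few patients with a resolved attributable cardiac DLT could not be re-treated, which is already the literal effect of 6.2 and 5.2. The DLT definition, the Part E stopping rule and all error rates stay as they are.
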